### **13.4.2.4 Gene Expression**

We will use differential gene-expression analysis to try to identify genes or sets of genes where change in expression levels correlate with response to study treatment.

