Study Outcome Measures	
Safety
 
 
• Common Terminology Criteria for Adverse Events (CTCAE) version 5.0
 
• Adverse events
 
• Serious adverse events
 
• Adverse events leading to discontinuation of study therapy
 
 
Efficacy
 
 
• Event-free survival
 
• Objective response rate → complete remission (CR) plus complete remission with incomplete hematologic recovery (CRi)
 
• Relapse free survival
 
• Duration of response
 
• Time to return of normal hematopoiesis
 
• Overall survival
 
• Proportion of patients who go on to receive allogeneic HSCT
 
 
Exploratory outcome measures
 
 
• Determine if MRD status can be used as a surrogate marker for survival
 
• Determine if using gene expression profiling can identify subset of patients who are more likely to respond
 

Rationale	
In the phase III trial of CPX-351 versus 7+3 chemotherapy for first line treatment of secondary AML in patients 60-75 years of age, 309 patients were treated with either of the two regimen. There was a statistically significant improvement in overall survival as well as overall remission rate in the CPX-351 arm.
 
Glasdegib in combination with LDAC has been shown to have tolerable side effect profile while improving survival outcomes in some patients with elderly AML who are unfit for chemotherapy. In the phase II trial of Glasdegib with cytarabine and daunorubicin, 69 patients with newly diagnosed AML were treated with the combination. The overall survival of the combination was improved to historical controls.
 
We hypothesize that the combination of CPX-351 with Glasdegib will demonstrate improvements in event-free survival as well as being well tolerated.

**Study Title: Phase II study of the combination of Glasdegib and CPX-351 in previously untreated patients with Acute Myelogenous Leukemia with MDS related changes or therapy-related Acute myeloid leukemia: A University of California Hematologic Malignancies Consortium Protocol (UCHMC1913/UCI 18-105)**

**PI:** [name], Assistant Clinical Professor of Medicine

**Institution:** Chao Comprehensive Cancer Center, University of California Irvine, Orange, CA

UCHMC1913/UCI 18-105  

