**SCHEDULE OF EVENTS**

Protocol Activity	Screening	Induction/ Re-induction E (Days 1-75)							Consolidation J (Days 1-55)				Maintenance K (Days 1-28)	EOT	Follow-up
	≤ 28 days prior to D1	D1	D3	D5	D6	Weekly (+/- 2 days)	Induction response D20 (+1 day)	Remission evaluation D28 to D60	D1	D3	D4	Weekly (+/- 2 days)	D1 (+/- 7 days)	Within 7 days of last dose	Every 3 month (+/- 14 days)
Informed Consent A	X														
Clinical Evaluation and Procedures															
Eligibility Review	X														
Disease Classification	X														
Medical History	X														
Concomitant Medication Review	X	For the entire duration of study participation													
AE/ SAE Review		From when participant start study therapy on induction day 1 up until 28 days after the last dose of study therapy/ and until resolution of any treatment-related AE/ SAE													
Physical Exam	X	X				X			X			X	X	X	X
ECOG Performance	X	X				X			X			X	X	X	X
12-lead ECG	X				X G	X G,H					X G			X	
ECHO	X														
BMA/BMBX	X C						X	X				X N		X L	
MRD (send to UW)							X	X						X L	
Cytogenetics /Molecular profiling	X C						X	X						X L	

Research sample for gene expression correlatives	X C, D						X D	X D						X D,L	
HSCT information/ Survival Status															X M
Laboratory Assessments															
Hematology	X	X				X	X	X	X			X	X	X	X
Chemistry	X	X				X			X			X	X	X	
Urinalysis	X														
Coagulation	X														
Pregnancy Test B	X								X				X		
Study treatment															
CPX-351 Infusion		X	X	X F					X	X					
Glasdegib					X I						X I		X		

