**Footnotes:**

- A Must be obtained before undergoing any protocol-specific study procedures, unless as part of standard of care
- B Serum beta-HCG should be done for any female of child-bearing potential
- C Bone marrow collections do not need to be repeated if a diagnostic bone marrow procedure was done prior to informed consent and is done within 28 days of starting day 1 of induction
- D Collect bone marrow aspirate for research sample for gene expression correlatives; if patient has any circulating blasts, then peripheral blood can be collected instead of aspirate; if bone marrow is a “dry tap,” then this sample does not need to be collected
- E Re-induction is based on response evaluation bone marrow done on day 20 of induction. If there is greater than 5% blast count, re-induction is recommended. The final decision for re-induction is based on investigator’s discretion. For patients who will be treated with re-induction, an ECHO and pregnancy test (for female patients of child-bearing potentials) will be done before starting re-induction
- F Omit CPX-351 on day 5 for participants receiving re-induction

G ECG is done pre-dose and can be done up to 24 hours before planned glasdegib dosing

H During induction, repeat an ECG a week after starting glasdegib (around day 13-15). If clinically significant abnormal ECG or clinically significant changes in QTc, then refer to section 6.4 for further guidance. If normal or non-clinically significant abnormalities and/or changes in QTc, additional ECG monitoring is not required and is done per the treating investigator's discretion

I Glasdegib should continue until day 1 of the next cycle of CPX-351

J Up to two cycles of consolidation is allowed. These are 28 day cycles, unless delays are necessary. In the case of a delay, glasdegib will continue daily until the start of CPX-351 infusion in the next cycle. If the patient will proceed to allogenic SCT, then consolidation can be skipped or shorten. Glasdegib will be stopped at least 7 days before transplant.

K These are 28 days cycle. Patients who are not receiving HSCT will be allowed to proceed to glasdegib maintenance for up to 1 year of study start

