### 1.7 Correlative Studies

In the non-intensive arm of the phase II trial with LDAC with Glasdegib, there were several genes that correlated with improved OS [26]. Lower levels of expression of FOXM1 and MSI2 and higher expression levels of BCL2 and CCND2 correlated with improved overall survival. In the intensive treatment arm with Glasdegib and cytarabine/daunorubicin, higher PTCH1 expression correlated with improved overall survival. Furthermore, in the intensive arm, mutations in FLT3, TP53, CEP170, NPM1 and ANKRD26 correlated with overall survival. Interesting to note, that patients with AML with mutated FLT3 (which is generally a poor risk group) did better than AML with wild type FLT3. Therefore, we will be measuring some of these genes to see if this observation of their correlation with improved overall survival is confirmed.

Furthermore, we will be measuring MRD at the end of induction by MFC at University of Washington. We would like to determine if MRD negative status at the end of induction correlated with survival outcomes in this patient population.

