## 2.3 Exploratory Objectives/ Exploratory Endpoints

2.3.1 Exploratory Objectives	2.3.2 Exploratory Endpoints

 
To determine if minimal residual disease (MRD) status can be used as a surrogate marker for survival
 
	
 
MRD status based on multiparameter flow cytometry from University of Washington will be collected at each response assessment time points
 

 
To determine if gene expression profiling can be biomarkers of response
 
	
 
Molecular, cellular and soluble biomarkers in peripheral blood and bone marrow samples will be collected
 

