#### **7.5 Correlative Studies**

In the non-intensive arm of the phase II trial with LDAC with Glasdegib, there were several genes that correlated with improved OS [11]. Lower levels of expression of FOXM1 and MSI2 and higher expression levels of BCL2 and CCND2 correlated with improved overall survival. In the intensive treatment arm with Glasdegib and cytarabine/daunorubicin, higher PTCH1 expression correlated with improved overall survival. Furthermore, in the intensive arm, mutations in FLT3, TP53, CEP170, NPM1 and ANKRD26 correlated with overall survival. Interesting to note, that patients with AML with mutated FLT3 (which is generally a poor risk group) did better than AML with wild type FLT3. Therefore, we will be measuring some of gene expression to see if this observation of their correlation with improved overall survival is confirmed.

Furthermore, we will be measuring MRD by MFC at the end of induction. University of Washington is the preferred facility who will receive the samples and assess MRD. If samples cannot be sent to University of Washington, sites should send their samples for MRD assessment according to their local institutional guidelines. We will determine if the status of MRD by MFC at the end of induction correlates with survival.

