#### **Gene Expression**

For gene expression testing, 2 mL will be collected from the bone marrow biopsy sample. In the event that there is a dry tap, the gene expression sample will be collected using peripheral blood if there are any circulating blasts present. If there are no circulating blasts, the gene expression sample will not be collected for testing. The sample needs to be processed immediately and carefully handled. Sites are responsible for providing their own tubes and vials for collection of all research related samples. In the event that a site does not have funding for supplies, the sample will not be collected and will not be considered a deviation. All samples will be shipped to and stored at UCI Clinical Trials Biospecimen Laboratory until analysis, which will be done at another laboratory. Please refer to the study sample lab manual for further processing, storage, and shipment instructions.

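### The only gene-expression analysis planned (13.4.2.4) tests change against response, which cannot identify likely responders and can track blast clearance; no analysis of screening expression is written

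*Combined protocol and SAP*

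**What the plan says.** Section 13.4.2.4 is a single sentence. It proposes differential expression analysis to find "genes or sets of genes where change in expression levels correlate with response to study treatment". It names no time points, no baseline analysis and no covariates.

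The aims are worded in three ways:

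- Study Summary, exploratory outcome measures: "Determine if using gene expression profiling can identify subset of patients who are more likely to respond".
- Section 2.3: "To determine if gene expression profiling can be biomarkers of response". The Study Summary objective is worded in the same way.
- Section 1.7, after listing FOXM1, MSI2, BCL2, CCND2 and PTCH1 expression: "we will be measuring some of these genes to see if this observation of their correlation with improved overall survival is confirmed". Section 7.5 repeats this almost word for word.

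The Schedule of Events row "Research sample for gene expression correlatives" puts samples at screening, at Day 20, at remission evaluation (Day 28 to 60) and, under end of treatment, at suspected relapse. Footnote D adds: "if patient has any circulating blasts, then peripheral blood can be collected instead of aspirate". Section 9.2 has a different rule: "In the event that there is a dry tap, the gene expression sample will be collected using peripheral blood if there are any circulating blasts". It leaves processing to a lab manual that is not part of the documents.

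**The concern.** A marker that picks out likely responders has to be measurable before treatment. Change from screening is not. The associations to be confirmed in 1.7 and 7.5 concern expression levels and survival, and 13.4.2.4 mentions neither.

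There is also a question of what change would measure. Response is itself defined largely by blast percentage. If the assay is run on unsorted cells, a responder's later sample is mostly normal marrow, while a non-responder's still contains leukemia. A gene expressed differently in the two cell types can then appear related to response through cell composition alone. Such genes could be reported as response biomarkers while the predictive and survival questions have no written analysis.

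**Working it through.** **Setting the text side by side**

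| Question in the plan | What it needs | What 13.4.2.4 supplies |
|---|---|---|
| Who is more likely to respond (Study Summary outcome) | Pre-treatment level against CR/CRi | Change against response |
| Are the cited survival associations confirmed (1.7, 7.5) | Level against OS | Nothing on level or OS |
| Biomarkers of response (2.3) | Not specified; on-treatment change could qualify | Change against response |

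Samples are scheduled at screening, so the gap is in the analysis and not in the sampling design.

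**Can change reflect blast content?** The plan gives no figure to reproduce, so this is an illustration.

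Inputs from the documents:
- 30 evaluable participants (13.3).
- CR/CRi rate 47%, from the cited phase 3 CPX-351 arm (1.5.3). This gives 30 × 0.47 ≈ 14 responders.
- Blasts below 5% for CR (10.2), carried into CRi by Appendix E.
- At least 20% blasts at diagnosis (Appendix A).

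Assumptions, not in the documents:
- Baseline blasts are uniform on 20-80%.
- Responders fall to 0-5%. Non-responders keep 0.3-1.2 times baseline, with a floor of 5%.
- Noise SD is 0.3, 0.5 or 0.8 log2 units per measurement. Noise on the change is then SD × √2, that is 0.42, 0.71 or 1.13.
- The gene is not regulated within any cell, and its baseline level is unrelated to response.

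Model: unsorted expression = f × R + (1 − f), where f is the blast fraction and R the blast-to-normal expression ratio.

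One case by hand, with R = 4 and baseline f = 0.50:
- Baseline: 0.50 × 4 + 0.50 = 2.50.
- Responder at f = 0.04: 0.04 × 4 + 0.96 = 1.12. Change = log2(1.12/2.50) = −1.16.
- Non-responder with blasts halved (f = 0.25): 0.25 × 4 + 0.75 = 1.75. Change = log2(1.75/2.50) = −0.51.

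For baselines of 20% and 80% the responder shifts are −0.51 and −1.60, against −0.30 and −0.63 when blasts are halved.

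Share of simulated trials with p<0.05 (Welch t-test, 2,000 per cell):

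| R | Change, SD 0.3 | Change, SD 0.5 | Change, SD 0.8 | Baseline level, all SDs |
|---|---|---|---|---|
| 1 | 4.9% | 4.6% | 4.9% | 4.5-5.1% |
| 2 | 65.3% | 32.0% | 14.9% | 4.2-4.9% |
| 4 | 99.8% | 89.0% | 53.1% | 4.6-5.7% |
| 8 | 100% | 99.8% | 90.7% | 4.5-5.3% |

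Sensitivity to the blast assumptions, with SD of the *change* set at 0.5 or 0.8:
- Baseline 30-80%, non-responders keeping 40-110% of it: 61% or 30% at R = 2; over 99% or 87% at R = 4.
- Baseline 20-80%, non-responders keeping 5-110% (floor 5%): 34% or 16% at R = 2; 88% or 57% at R = 4.

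These ranges are not bounds. The noisiest assay combined with the widest spread of non-responders would go lower.

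**Sample source.** Footnote D lets blood stand in for marrow whenever blasts circulate. CR requires that none circulate (10.2). A responder may therefore contribute screening blood and remission marrow, so the tissue difference is linked to outcome. Patients who die before a second sample have no change value.

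**Dry tap.** Under footnote D a dry tap means the sample is not required. Under 9.2, blood is taken if blasts circulate. The two rules conflict.

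**The case against.** The strongest defence has four parts.

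1. The formal objective in 2.3 asks only about biomarkers of response, which on-treatment change can serve. This stands. A reader might infer that the plan cannot answer its gene-expression objective at all; the documents support that only for the Study Summary outcome measure.
2. Differential expression analysis often means comparing levels between groups, and *change* may have been used loosely for a responder/non-responder difference. This is possible, but the sentence says change and names no time points, so it needs rewording on either reading.
3. Section 13.4.2.1 allows many further analyses, and 13.4.2.3 provides Kaplan-Meier, log-rank and Cox methods into which expression against OS would fit. This permits the missing analyses, but neither section names one.
4. The lack of sorting is inferred from silence, since processing sits in an unseen lab manual. This also stands. A reader might conclude that the change analysis mainly measures blast clearance, or that every gene differing between blasts and normal cells must correlate with response. The documents do not establish unsorted samples, and the effect depends on the gene: absent at R = 1 and modest at R = 2 with noisy data.

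It is also tempting to allow blood only after a dry tap. That could lose baseline samples. Footnote C, attached to the research-sample row, waives a repeat marrow when a diagnostic one was done within 28 days of Day 1, so blood may be such a patient's only screening research sample.

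**Conclusion.** The concern holds as a mismatch between analysis and aim. The one written analysis uses a quantity known only after treatment. It cannot serve the predictive outcome in the Study Summary and does not address expression level against OS in 1.7 and 7.5. That conclusion rests on the text alone.

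The composition artefact is real but conditional. If samples are unsorted and unadjusted, a non-predictive gene reaches p<0.05 in roughly 15-65% of trials at a 2-fold ratio and 53-100% at 4-fold, about 5% at ratio 1, and about 5% in every case when baseline level is tested. Fold ratio, noise and blast fractions are assumed, and the figures are for a single gene without correction.

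The consequence is limited to an exploratory objective. The primary endpoint and its decision rule are untouched.

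**What to change.** In 13.4.2.4:

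- Make screening expression the predictor of CR/CRi and, for those genes named in 1.7 that are measured, of OS. Report this as exploratory, with either the number of genes tested or a false-discovery-rate adjustment.
- Keep change from screening as a separate descriptive pharmacodynamic analysis, with named time points, same-tissue pairs only and blast percentage as a covariate.
- Record sample source (marrow or blood) and include it in the model. Do not restrict blood sampling at screening.

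Separately, reconcile footnote D with 9.2 on what is collected after a dry tap.

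The cost is mainly wording. Screening samples and marrow assessments are already scheduled, although 9.2 lets a site without supply funding skip the research sample, so some baselines will be missing. The change analysis will have fewer usable pairs, and there is slightly more analysis work.

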### **13.4.2.5 Analyses of Intolerability or Toxicity**

We will examine the data to discover factors that may predict adverse reactions to the study treatment. We will proceed in the same way as outlined above for secondary analyses. Adverse events will be classified by type, frequency, severity, timing, grade, and other factors that may aid interpretation, and be summarized by proportions, overall and within groups of subjects.

## **14.0 STUDY MANAGEMENT**

---

### **14.1 Conflict of Interest**

Any investigator who has a conflict of interest with this study (patent ownership, royalties, or financial gain greater than the minimum allowable by their institution, etc.) must have the conflict reviewed according to their local conflict of interest policy. If there is a positive disclosure, the site must communicate this information to the initiating site to determine if any revisions to the consent form are required with the IRB of record based on the COI outcome.

### **14.2 Regulatory Issues**

Regulatory requirements both at the federal level and the institutional level must be followed. The federal regulations for human subject protections and for clinical trials can be found in the

Federal Code of Regulations for the Department of Health and Human Services (DHHS) and the websites for federal agencies such as the National Institutes of Health (NIH) and the Food and Drug Administration (FDA).

### **14.3 Scientific Review Committees**

Each participating institution must submit the protocol to their individual scientific review committees per their institutional policies. Scientific Review Committee approval is required prior to IRB approval through individual IRBs and reliance on the initiating site's IRB. Site may rely on Scientific Review Committee approval by another NCI designated cancer center.

### **14.4 Institutional Review Boards**

Each clinical site must obtain approval by their local Institutional Review Board (IRB) prior to the initiation of any UCHMC clinical trial. Communication between a site and the respective IRB is the responsibility of the site investigator. Copies of IRB correspondence, including protocol approval letters, must be kept on file at the site. A site may begin accrual upon contacting the Clinical Trials Operations Core by e-mail to assure any outstanding regulatory issues have been addressed and resolved. The UCHMC Clinical Trial Operations Core will be responsible for ensuring that all necessary essential documents as listed below in the trial master file are in place and kept up to date throughout the study. It is not required to wait until all UCHMC sites secure local IRB approval to begin enrolling at an approved site. Each site is responsible for the annual renewal of IRB approval if not operated through UC Reliance. Each investigator must report to the IRB any problems, serious adverse drug reactions or proposed changes in the protocol that may affect the status of the investigation and the willingness of patients to participate in the trial. The investigator must also report to the IRB at intervals appropriate to the degree of risk in the study, but no less frequently than once a year or at study closure.

### **14.5 SMART IRB Process**

The initiating site's IRB will act as IRB of record through the SMART IRB reliance agreement.

#### **14.5.1 Initial Review Process**

1. All relying PIs agree to reliance through the SMART IRB process
2. The initiating site PI will proceed with local IRB submission and notify the initiating site's IRB about the participating sites
3. Reviewing IRB approves the study
4. IRB approved documents are pulled by the initiating site and distributed to the participating sites
5. Each participating site will begin their local IRB submission and obtain approval and acceptance of the reliance
6. Once accepted, the smart IRB agreement will be finalized and distributed to the sites

#### **14.5.2 Continuing Review**

Continuing Reviews (Annual Reviews) are the responsibility of the Reviewing PI. If the Continuing Review approval is not obtained in a timely manner, none of the relying sites will be allowed to continue research. The initiating site will inform the relying sites once the Continuing Review approval has been granted.

If the participating sites are relying on the initiating site's IRB, participating sites are to provide the initiating site of all requested documents and information approximately 120 days prior to the expiration date of the study. Sites utilizing their local IRB must submit the continuing review approximately 90 days prior to expiration date of the study. Once the Continuing Review has been approved, the initiating site will update the expiration date in OnCore. Any sites utilizing their local IRB must submit their continuing review approval to the lead site upon receipt by sending the form to [contact].

The Office of the President notes: "... no relying UC site on your study will be able to continue work if you don't obtain IRB renewal [continuing review approval] on time: it is your responsibility as a Reviewing Campus PI to apply for the renewal [continuing review] on time!"

